15. ETHICAL CONSIDERATIONS

This study should be conducted in accordance with the protocol and Good Clinical Practice (GCP) guidelines, as described in the ICH Harmonised Tripartite Guidelines for Good Clinical Practice 1996.

By signing this protocol, the investigator agrees to follow the instructions and procedures described in the protocol and will therefore comply with the principles of Good Clinical Practice on which it is based, bearing in mind the Declaration of Helsinki <http://www.unav.es/cdb/ammhelsinki2.html>.

All patients will go through a therapeutic condition. In the case of "sct" therapy, the efficacy is proven by previous research and trials (Glina et al., 2007. Rodriguez et al., 2019) and, in the case of combined therapy, the health risk is minimal and the probability of its efficacy is at least equal to that of "start-stop" therapy since, in this case, the former encompasses the latter.

The data collected will be subject to the data protection law: Organic Law 15/1999 of 13 December on the Protection of Personal Data (LOPD). And the informed consent is collected in accordance with the Royal Decree 223/2004 of February 6.

16. DURATION OF THE TREATMENT

The duration of the treatment will be 7 weeks, during which the previously-explained exercises will be carried out.

17. EVALUATION AND SAFETY OF THE TRIAL

The products to be used in the research will be safe and their responsible use will not produce any adverse reactions.

A personal data file will be created, to be owned by the Sexological Institute of Murcia; its sole purpose will be the collection of the data from the trial and its subsequent study. A backup copy of the data and its recovery procedures will be stored separately to the computer system involved in the trial.

Each subject will be assigned a random, statistically-generated, numerical or alphanumerical code.

The person responsible for the file and/or its processing will guarantee that only he or she has access to the data and its subsequent processing.

Confidential data will be encrypted with an encryption algorithm and a key which will ensure that the data is unreadable without prior knowledge of the key.

Non-automated files shall be stored in cabinets or document filing cabinets, which, in turn, shall be stored in an area with access protected by lockable doors.

The lubricants used are made from harmless ingredients. There should be no problems in case of ingestion. However, in case of irritation the patients will be instructed to stop using it and will be excluded from the investigation. Participants will be informed about the ingredients before use and will all be instructed to carry out a small tolerance test on their arm before use in the genital area.

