5. SUMMARY

5.1. *Identification of the promoter*

Sexological Institute of Murcia (ISM)
[name]
Teléfono: [name]
N.I.F [name]

5.2. **Title of Clinical Trial**

A randomized closed trial (RCT) to compare the effectiveness and safety of a masturbation aid's exercise protocol as a first-line treatment for patients with primary premature ejaculation.

5.3. **Protocol ID Code**

Protocol ID Code: ISM-SCT-2019-01

5.4. **Lead Researcher**

[name]
Director, Sexological Institute of
Murcia
[name]

5.5. **Location of trial**

The trial will be conducted in the following Clinic:

1. Sexological Insitute of Murcia
[name]
[name]. [contact]

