10. MAIN OBJECTIVE

The aim of the project is to demonstrate the effectiveness on PE of the "sct" combination treatment adapted from Semans (1956) within the framework of an exercise program carried out with an new external device specific design for this method .

Its effectiveness on PE will be reflected in increased intravaginal ejaculation latency times (IELT) and subjective perception scores from baseline therapy. The increased efficacy of the combination therapy ("sct" in conjunction with external device) will be reflected in the greater increase in IELT and subjective perception scores from combination therapy over "sct" therapy. The level of scientific evidence will indicate the competitiveness and efficacy of this cognitive-behavioral psychological technique.

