19. INTERVIEWS, QUESTIONNAIRES OR INSTRUMENTS TO BE USED IN THE TRIAL

The IELT measurements will be collected by self-registration after each week of treatment (APPENDIX I).

In order to collect the information regarding the perception of ejaculation, the Premature Ejaculation Profile (PEP) will be used (Patrick et al., 2009), a self-reported instrument consisting of four measurements (perceived control over ejaculation, personal stress related to ejaculation, satisfaction with sexual relationships, and interpersonal difficulty related to ejaculation). These will give an overall profile and score (Patrick et al., 2009), where the lowest scores express the lowest performance. The reliability coefficient between ranges from 0.66 to 0.83 and its validity was contrasted with dapoxetine and Intravaginal Ejaculation Latency Times (IELT). This instrument was validated in American and European trials, with people from Germany, France, England, Italy and Poland involved (Giuliano et al., 2008) although it has been used also in the Spanish community (Bar-Or, Salottolo, Orlando, Winkler, & Group, 2012; Buvat, Tesfaye, Rothman, Rivas, & Giuliano, 2009).

The Premature Ejaculation Diagnostic Tool (PEDT) will be used for the diagnosis. It takes five measurements in order to evaluate difficulty in delaying the ejaculation, ejaculation occurring before the patient wanted it, ejaculation with little stimulation, frustration related to premature ejaculation, and the couple's opinion about ejaculation. The test-retest reliability is 0.82 and all values statistically distinguish and differentiate statistically between PE and non-PE patients.

The Golombok-Rust Inventory of Sexual Satisfaction (GRISS) will also be applied. This is a brief 28-question questionnaire to assess the existence and severity of sexual problems in both members of a heterosexual relationship (Rust & Golombok, 1985, 1986). This questionnaire provides separate scores for men and women on 3 shared scales (avoidance, non-sensitivity, and dissatisfaction) and 6 gender-specific scales (impotence, premature ejaculation, anorgasmia, vaginismus, infrequency, and lack of communication) with acceptable values of reliability and validity (Rust & Golombok, 1985, 1986). The instrument was validated in the English community and is already being used in Spain in the official Master's degree in Sexology at the University of Almeria (García González, 2013; López Lorente, 2013).

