Waldinger, M. D., Zwinderman, A. H., Olivier, B., & Schweitzer, D. H. (2008). Geometric Mean IELT and Premature Ejaculation: Appropriate Statistics to Avoid Overestimation of Treatment Efficacy. *The Journal of Sexual Medicine*, 5(2), 492–499

Collaborator's signature:
Instituto Sexológico Murciano

INSTITUTO SEXOLOGICO MURCIANO
N.R.S 20300055
[contact]
www.isemu.es | [contact]

Lead Researcher's signature
[name]

Annexed 1

Data collection forms

REGISTER OF EJACULATION TIMES

[figure not shown]
[figure not shown]
[figure not shown]
[figure not shown]
[figure not shown]
[figure not shown]
[figure not shown]
[figure not shown]
[figure not shown]
[figure not shown]
[figure not shown]
[figure not shown]

[figure not shown]
WEEK:

NAME:

MONDAY TUESDAY WEDNESDAY THURSDAY FRIDAY SATURDAY SUNDAY

[figure not shown]
[figure not shown]

[figure not shown]

[figure not shown]
[figure not shown]
[figure not shown]
[figure not shown]
[figure not shown]
[figure not shown]

MASTURBATION

Record the time you take to ejaculate when masturbating

[figure not shown]
PENETRATION INTERCOURSE

Record the time you take to ejaculate after penetration

Annexed 2

ANEXO 2

[figure not shown]

PARTES.

1 – Pines magnéticos de carga

2 – Rosca hembra para aplique de manos libres.

- 3 – Rosca reguladora de succión.
- 4 - Botonera para control de vibración y calefacción.
- 5 – Conexión con resistencia calefactora
- 6 – Orificio de entrada de la manga
- 7 – Motor vibrador
- 8 – Bolsillo para albergar el motor vibrador.
- 9 – Palo calefactor.
- 10 y 11 – Sistema de imanes para asegurar el cierre.

**DIMENSIONES
PRINCIPALES**

MATERIALES Y PESO

PARTE	MATERIAL
MANGA	TPE (Elastómero termoplástico)
CUERPO	ABS
PALO CALEFACTOR	
RECUBRIMIENTO DEL CUERPO "SOFT TOUCH"	PDMS ("Silicona soft touch")

[figure not shown]
PARTE	PESO (gramos)
MANGA	340
MYHIXEL I (con manga)	670

MYHIXEL I (en uso, sin calefactor)	560
------------------------------------	-----

ELECTRONICA Y FUNCIONES

PARTE	MATERIAL
BATERÍA	POLÍMERO DE LITIO (650 Ma 3.7 V)
MOTOR VIBRADOR	~2 V (3.5 mm y 100 HZ)
CALEFACCIÓN	RESISTENCIA EN POLIAMIDA
CARGA	PINS MAGNÉTICOS + USB

1	2	3	4	5	6
LED 1+2	LED 1+2	LED 1+2	LED 1	LED 1	LED 2
CARGANDO	CARGADO	BATERÍA BAJA	CALENTANDO	TEMPERATURA ALCANZADA	VIBRACIÓN
Leds ON fijo	Leds OFF	Los leds parpadean alternativamente	Led ON Latente (ver link adjunto)	Led OFF	Led On Durante 10 sg y luego OFF

COLOR LEDS (1 y 2): **BLANCO CÁLIDO**

APPENDIX 3

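### The title promises a safety comparison, but the readable protocol plans no systematic collection of harms, and Section 17 asserts the result in advance while foreseeing irritation

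*Protocol*

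**What the plan says.** The title (Protocol, Section 5.2) gives the trial two comparative aims: "compare the effectiveness and safety of a masturbation aid's exercise protocol as a first-line treatment".

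Section 17 is the only section on safety. It opens with a statement of fact: "The products to be used in the research will be safe and their responsible use will not produce any adverse reactions". Most of the rest concerns data protection. The last paragraph turns to the lubricant: participants are told the ingredients and do a small tolerance test on the arm, and "in case of irritation the patients will be instructed to stop using it and will be excluded from the investigation". The section does not define an adverse event or say how one would be asked about, recorded or reported.

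For data collection, Section 19 says: "The IELT measurements will be collected by self-registration after each week of treatment". It also names three questionnaires: PEP, PEDT and GRISS. The register in Annexed 1 asks for ejaculation times, for example "Record the time you take to ejaculate after penetration".

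**The concern.** A trial that names safety in its title needs some means of observing harm in both arms. Here the one safety section gives the answer as a premise, and no form in the readable text would let the data confirm or contradict it. The exercises are done at home for 7 weeks, so a problem that is not asked about is unlikely to be seen by staff. Only group 2 uses the device, so group 1 is the natural comparator, but no comparable question is put to group 1 either. Section 12 lets men leave at any time and expects many to do so, without asking why, so a man who stops because of a problem looks like any other dropout.

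At stake is the standing of any later statement that the device caused no problems. The device's manufacturer funds half of the project (Sections 6 and 19), so a safety statement with no measurement behind it would be open to easy challenge. The efficacy comparison is not affected.

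**Working it through.** The protocol states no safety figure, so there is none to reproduce. The check is a reading of every place where harms could enter the plan, followed by a short illustration.

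**1. Where safety could appear**

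- Title (5.2): effectiveness and safety are to be compared.
- Objectives (5.7 and 10): effectiveness only. Section 10 opens: "The aim of the project is to demonstrate the effectiveness on PE".
- Evaluation parameters (11): IELT, perception of ejaculation, and sexual satisfaction. No safety variable.
- Analysis (14): fold change of IELT, and contrasts between groups and against baseline. No safety variable.
- Instruments (19): IELT self-register, PEP, PEDT, GRISS. The domains described are control, distress, satisfaction and sexual function, not pain, skin reaction or injury.
- Budget (6): also licenses MCMI-III, which Section 19 omits. Nothing in the protocol describes it as a measure of harm.
- Register (Annexed 1): the readable fields are week, name, weekday, time to ejaculation in masturbation and time to ejaculation in intercourse.
- Withdrawal (5.11 and 12): dropout is expected, and no reason is requested.

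Safety therefore appears in the title and in Section 17, and in no place that generates data.

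**2. Section 17 against itself**

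The opening sentence rules out adverse reactions under responsible use. The last paragraph provides for irritation and for a tolerance test. Both cannot stand as written. The stated consequence of irritation is that use stops and the man is excluded. No recording is stated, so the one harm that is foreseen may leave the dataset along with the man.

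**3. What non-collection would hide (illustration)**

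The protocol gives no harm rate, so a range is assumed. The planned total is 50 (5.11). Equal allocation is also an assumption, since no ratio is stated, and gives 25 per arm. The chance of at least one affected man in an arm is 1 − (1 − p)^25:

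- p = 2%: 1 − 0.98^25 = 40%
- p = 5%: 1 − 0.95^25 = 1 − 0.277 = 72%
- p = 10%: 1 − 0.90^25 = 93%
- p = 20%: 1 − 0.80^25 = 99.6%

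At any of these rates, the readable register has no field in which to enter the case.

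**4. What zero events would show, even with full recording (illustration)**

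The exact two-sided 95% upper limit with 0 events in n men is 1 − 0.025^(1/n).

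- n = 25: 1 − 0.025^(1/25) = 13.7%
- n = 17: 1 − 0.025^(1/17) = 19.5%. Here 25 × 0.7 = 17.5, taken as 17, which assumes that everyone in the 30% for dropout or non-compliance is lost.

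These limits reflect the small arms, not the missing collection, and they would be the same after the fix. They show only that the opening sentence of Section 17 could not be established by this trial, even if no event were recorded.

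**The case against.** Several points on the other side have force.

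- **Irritation is foreseen.** Someone must learn of a case in order to exclude the man, so cases could come to light as exclusions. This stands. A reader might infer that the trial must end with no events in either arm by construction, and the text does not support that. What it supports is that there is no systematic collection.
- **No formal safety conclusion is planned.** The objectives, parameters and analysis are silent on safety. This also stands. A reader might infer that the trial would produce a false finding of safety, but that presupposes harm, which the documents do not show. The accurate word is unsupported.
- **The device's hazards.** Annexed 2 lists a control described as "Botonera para control de vibración y calefacción" (for vibration and heating) and a suction regulator, so a reader might infer a demonstrated heat or suction risk. However, the sheet gives the in-use weight without the heater, and the Appendix 3 steps mention none of these functions. They are possible exposures and no more.
- **Loss.** The 30% covers dropout or non-compliance together. A non-compliant man can still report a problem, so 30% should not be read as men lost to observation.
- **Completeness.** Parts of Annexed 1 are figures that could not be read, Section 7 was not available, and the MCMI-III entry shows that the Section 19 list is not exhaustive. The absence is established for the readable text only. The form's title and fields and the instrument list all agree with it.
- **The analysis plan may cover it.** This does not stand. An analysis plan can specify how harms are tabulated, but it cannot supply data that no form collects.

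**Conclusion.** The point holds for the readable protocol. The title promises a safety comparison, no planned variable, listed instrument or readable form field asks about harm, no reason for leaving is requested, and Section 17 states the outcome in advance while providing for a reaction it says will not occur. As the plan stands, harms could surface only incidentally, and any conclusion on safety would be unsupported in either direction.

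The defect itself cannot be sized, because the documents give no harm rate. The limits of 13.7% (0 of 25) and 19.5% (0 of 17) are illustrations. Both assume equal allocation, and the second also assumes that the whole 30% is lost. The point should be corrected before the trial starts, but it does not touch the efficacy comparison.

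**What to change.** Add a short harms item to the weekly Annexed 1 register.

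- Core questions, identical in both arms: any genital pain, skin or other problem; its severity; its duration; and whether the exercises were interrupted.
- For group 2 only: which device functions were in use.
- For any man who stops: the reason for leaving.

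Report counts per arm among all randomised men, including those excluded. Replace the opening sentence of Section 17 with a statement that adverse reactions will be recorded and reported, and reconcile it with the irritation paragraph. How irritation is managed is for the investigators; the point here is only that each case is recorded.

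If the sponsor prefers not to collect this, remove the reference to safety from the title and draw no safety conclusion.

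The cost is a slightly longer form that is already due every week, one descriptive table, and a less favourable safety statement than the present one.

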18 RES: 40002570

5.6. **Ethics committee and participating clinics.**

This trial has been submitted for the approval of the Ethics Committee in the following establishment:

- Hospital José M^a Morales Meseguer – Murcia

The following clinics will take part in the trial:

- Sexological Institute of Murcia, Spain

5.7. **Main objective**

Assess the effectiveness of a cognitive-behavioral program called Sphincter Control Training (SCT), within an app for android systems, as treatment of primary premature ejaculation in Spanish population and determine if said program is enhanced with the use of a device to help masturbation specially designed for the same..

5.8. **Design**

-This research project will use two experimental groups. One will be given the "SCT" therapy on its own (experimental group 1) and the other will be given the "SCT" therapy combined with the aforementioned device (experimental group 2). The subjects in both groups will experience parallel therapy with the same exercise protocol (with the only difference being that, in experimental group 2, the SCT exercises will be carried out with the device in question). The participants who meet the selection criteria will be randomly assigned an experimental group, along with its corresponding conditions.

5.9. **Illness or condition under investigation**

Primary Premature Ejaculation (F52.4).

5.10. *Information regarding the device under investigation and the exercise program.*

Device under investigation: Myhixel I.

Dimensions

Length: 4,45 Inches (113 mm)

Width: 4,45 Inches (113 mm)

Height: 8 Inches (203 mm)

Diameter 3,58 Inches (91mm)

Weight 22,22 Oz (630 grams) with lid

19,75 Oz (560 grams) while using

Materials

Thermoplastic Elestomer

[figure not shown]
ABS

Silicone

Type of Battery Lithium

Charger Type USB + Magnet (Waterproof)

DATA SHEET ANNEXED 2

Exercise program: SCT.

The home exercise program includes 4 activities:

The first exercise called "Discovering your pelvic floor" will be carried out for one week, the second, called "Stop and Start", should be carried out for 3 weeks. The third is called "Stop and Start constant stimulation" and should be carried out for 2 weeks, and the last exercise in the program, "Stop and Start, constant stimulation with coital movements" will be carried out for a week.

Exercise information APPENDIX 3

Lubricant to be used in the trial: Myhixel lube.

Content: 50 ml (1.69 Oz)

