Ingredients: Water, Propylene Glycol Hydroxycyclulose, Sodium Benzoate, Polysorbate 20, Potassium Sorbate, D-limonene, Sodium Hydroxide, Carica Papaya

Fruit Extract, Chamomilla Recutita, Flower Extract, Citric Acid, Plankton Extract, Perfume, Sodium Citrate, Citral, Soluble Collagen.

5.11. **Sample group and number of participants.**

The sample group will be heterosexual men, aged 18 or older, taken from all over the country. They all suffer from primary premature ejaculation, haven't received any treatment for the condition in the past, and have had a stable partner for at least 3 months before the start of the trial.

A sample size of 50 patients is expected. We estimate a 30% dropout or non-compliance during the study.

5.12 **Schedule and proposed end date**

Duration of the inclusion period: June 2019 - August 2019

Planned trial start date: July 2017

Planned trial end date: September 2017

5.13. **Financing**

Funding will be provided by the research area of the Sexological Institute, Murcia, Spain, and the NEW WELLNESS CONCEPT SL.

6. **RELEVANT FINANCIAL ASPECTS OF THE TRIAL**

50% of the project's funding will be provided by the research area of the Sexological Institute, Murcia, Spain, while the other 50% will be funded by the NEW WELLNESS CONCEPT SL.

This 50 % includes the provision of 30 Myhixel I devices and 30 bottle of lubricant Myhixel lube.

FINANCIAL REPORT ON THE PROJECTED EXPENDITURE OF THE RESEARCH PROJECT:

Title: **PROTOCOL INVESTIGATION: MYHIXEL**

Research code: **ISM-SCT-2019-01**

Lead Researcher: **[name]**

Promoter: **Sexological Institute, Murcia, Spain**

DETAILED DESCRIPTION OF PROJECTED FUNDED COSTS

COSTS PERSONNEL:	
1 Part-time Research Intern	400,00 €/month *
SUBTOTAL PERSONNEL:	1.200 ,00 €
FACILITIES, MATERIALS, SOFTWARE LICENSES AND TESTS:	
Licenses and correction kit MCMI-III, PEP, PEDT y GRISS male.	66,49 €
1 monthly license IBM SPSS statistics software.	88,50 €
MRW Courier Service ecommerce National Transport 30 kits	275,10 €
SUBTOTAL FACILITIES AND EQUIPMENT:	430,09 €
CONSUMIBLES:	
50 Myhixel lubricant (HOLE LOTION)	480,00 €
30 Myhixel Device	990,00€
SUBTOTAL CONSUMIBLES:	1470,00€

OTHER COSTS: (specify details of costs and amounts paid)	
Domain and hosting, web landing page for trial, yocontrolo.org, Arsys S.L.U.	101,41€
Online templates Web Templates Ltd	67,00 €
SUBTOTAL OTHER COSTS:	2043,91 €
TOTAL PROJECT BUDGET:	5.419,10 €

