SCT Exercise Program PATIENT FORMS

In the first week, we're going to start with what we call the **Stop and Go Flip Hole Program**.

OBJECTIVES

1. To become aware of the role of the pelvic floor in the orgasmic response.
2. To identify the pattern of muscle tension in the genital area that's necessary to ejaculate.
3. To identify the voluntary nature of that pattern of muscular tension that's necessary to ejaculate.

KEY POINTS

Perform the activity only after you've watched the video that corresponds to the activity Discovering the Pelvic Floor.

This activity is carried out individually.

Before carrying out the activity, the participant must understand its theoretical content.

It should be carried out a minimum of 4 times or until the participant is able to reach the objectives of this first week.

This activity isn't just about masturbation, but rather about becoming aware of the role of the pelvic floor.

STEPS TO FOLLOW

Find a quiet moment where you can't be interrupted. Turn off your phone, TV, and radio, and don't let children or other people living with you distract you.

Before you start, apply a few drops of lubricant to the Flip Zero device, which you will find in the kit. Start to caress your penis, slowly and progressively, until you get an erection. From this point you will start to masturbate using the Flip Zero device, paying attention to the changes that occur around the genital area and in the nearby muscles.

It's important that you try to identify how muscle tension increases in the genital area and muscles near it as your excitement increases. You must consciously identify these points of muscular tension or tightness in the legs, abdomen, buttocks and especially in the pelvic floor (under the testicles and in the anal sphincter).

Continue masturbating until you ejaculate and observe that in order to provoke the ejaculatory reflex, you don't only need to stimulate the penis, but you also need to create muscular tension in the area, and especially in the pelvic floor.

We can see, therefore, that muscular tension in the pelvic floor area is a necessary condition for ejaculation, and it is also a voluntary factor. This muscular group is the key to either delaying or accelerating the ejaculatory reflex.

If this muscle group, known as the pelvic floor, and especially the anal sphincter and the urethra, are not in tension, the ejaculation reflex cannot occur.

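### Section 17 removes randomised men with lubricant irritation from the trial, ending their outcome and harm follow-up although the title promises a safety comparison

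*Protocol*

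**What the plan says.** Section 17 gives two instructions for irritation from the lubricant: "in case of irritation the patients will be instructed to stop using it and will be excluded from the investigation". The first concerns the product and the second concerns trial participation. The same section opens with a statement about harm: "The products to be used in the research will be safe and their responsible use will not produce any adverse reactions". It also asks all participants to try the lubricant on the arm before genital use, without saying whether this comes before or after randomisation.

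The title in Section 5.2 describes a trial "to compare the effectiveness and safety of a masturbation" aid's exercise protocol. Section 5.8 places allocation at entry: "The participants who meet the selection criteria will be randomly assigned an experimental group". Section 13 does not list irritation or lubricant intolerance among the exclusion criteria. Section 10 makes the comparison between arms central: the added value of the device "will be reflected in the greater increase in IELT and subjective perception scores from combination therapy over" SCT alone.

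On who receives lubricant, Section 6 gives two figures. The description of the company's contribution reads "This 50 % includes the provision of 30 Myhixel I devices and 30 bottle of lubricant Myhixel lube", and the courier line is for 30 kits. The consumables line reads "50 Myhixel lubricant (HOLE LOTION)". The patient forms in Appendix 3 pair lubricant with the device, for example "apply a few drops of lubricant to the Flip Zero device, which you will find in the kit".

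**The concern.** Irritation that appears during the exercises is a post-randomisation event and may be caused by what the man was given. Removing him for it means that the men still observed in each arm are no longer the groups formed by randomisation. If the removals fall unevenly, the comparison of fold change in IELT and of the subjective scores is made between selected groups.

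There is a second loss on safety. Irritation is the one reaction that Section 17 foresees, and the rule ends observation at the moment it occurs. Its course and any later problem in that man are not followed. A statement written in advance that responsible use causes no reactions sits badly beside a title that promises to compare safety.

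**Working it through.** **Sequence of events.** Men meet the criteria and are allocated (Section 5.8). They then do seven weeks of exercises (Section 16), with lubricant at least in the forms written for device users (Appendix 3). Irritation in use therefore falls after allocation, and Section 17 ends participation there. No other section says that such a man stays in follow-up or is counted in his arm.

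**When this biases the comparison.** Let a share q of an arm be removed, and let those men be k SD worse on outcome than the men retained. The full-arm mean is m − qk and the retained mean is m, so that arm is overstated by qk. The bias in device minus SCT alone is

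q₂k₂ − q₁k₁.

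It is zero if the two products are equal, positive if removals of poorer responders concentrate in the device arm, and negative if the removed device users would have done better than the rest. The Protocol supplies none of the four quantities.

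**Scale for reference.** Section 12 states 24 per group, power 0.80 and alpha 0.05, but no effect size or SD, so the 24 cannot be reproduced forward. Solving backward with two-sided alpha (Section 14): d = √(2/24) × (1.960 + 0.842) = 0.81 (0.83 with the t distribution).

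**Illustration (all q and k assumed; removals in the device arm only; 24 per arm).**

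- q = 0.05, k = 0.5: bias 0.025 SD, 3% of 0.81; two-sided type I error 0.051.
- q = 0.10, k = 1.0: bias 0.10 SD, 12% of 0.81; type I error 0.063.
- q = 0.20, k = 1.0: bias 0.20 SD, 25% of 0.81; type I error 0.100.

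Type I error is Φ(−1.96 + b/se) + Φ(−1.96 − b/se), with b = qk and se = √(1/24 + 1/(24(1−q))). For the last line se = √(1/24 + 1/19.2) = 0.306 and b/se = 0.65.

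On the fold-change scale, the ratio of retained to full geometric mean is exp(qδ), where δ is the log difference. With q = 0.10 and δ = 0.4 (fold change 33% lower) it is exp(0.04) = 1.04. With q = 0.20 and δ = 0.7 (50% lower) it is exp(0.14) = 1.15. These values too are assumed.

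**Number of men.** With 50 enrolled (Section 5.11), an equal split gives 25 per arm. An assumed irritation risk of 5%, 10% or 20% gives 1.25, 2.5 or 5 expected removals from one arm. The chance of at least one, 1 − (1 − p)²⁵, is 72%, 93% or 99.6%. The 30% loss in Section 5.11 leaves 50 × 0.70 = 35 men, about 17 per arm.

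**What zero events could show.** The one-sided 95% upper limit for zero events in n men is 1 − 0.05^(1/n). For n = 25 it is 0.113 and for n = 17 it is 0.162.

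**The case against.** The strongest objection is about exposure. The budget lists 50 lubricants, which equals the planned sample. Section 17 addresses the arm test to all participants, and Section 19 names the lubricant for the trial without naming an arm. If both arms use it alike and irritation relates to outcome in the same way, the efficacy bias is about nil. This stands. A reader might infer that only the device group loses men and so keeps only those who tolerated the product. The Protocol does not settle that, because its supply figures conflict.

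Second, removal may mean withdrawal, with earlier data kept and the reason noted; staff must learn of the irritation in order to act on it. This also stands. A reader might infer that the safety result would be near zero by construction. The text does not say that events go unrecorded, and the rule covers lubricant irritation only, not other harm from the device. Much of the register in Annexed 1 is not visible, so it cannot be said to lack a field for harms. Even on the withdrawal reading, follow-up of a randomised man ends.

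Third, the arm test might screen out some men before allocation. Its timing is not given, and it cannot be assumed to catch all irritation arising in genital use.

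Fourth, an SAP that is not shown may define the analysis set. It could keep such men in their arm, but it cannot recover measurements that the Protocol tells staff to stop taking.

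Fifth, the opening statement on reactions is limited to responsible use, and the section goes on to allow for irritation. It is therefore not a flat denial of harm. It still states in advance something the trial is meant to examine.

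**Conclusion.** The point holds for the removal rule itself. As written, it ends outcome and harm follow-up of randomised men because of an event that may be related to treatment, in a trial titled as a comparison of safety. This does not depend on any assumed figure.

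Bias in the device comparison is possible but not established. It requires irritation to differ by arm, or to relate differently to outcome by arm. That is likely if lubricant goes mainly with the device and about nil if both arms use it alike. The range of 0.025–0.20 SD, or 4–15% on the fold-change scale, rests wholly on assumed rates and outcome differences with removals in one arm only. Its lower end is negligible, and the direction is also an assumption.

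The 11% limit for zero events in 25 men needs no such assumption. It does not concern the removal rule; it shows that a trial of this size could not support the advance statement about adverse reactions even with a clean record.

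**What to change.** Leave the instruction on product use to the sponsor. In Section 17, replace the clause on removal with wording such as: the man remains in follow-up, continues the weekly register and the questionnaires, and is analysed in the group to which he was randomised. Record irritation in both arms, using a line on the weekly register if it has no such field, and report counts by arm with exact confidence limits. Delete the opening statement about adverse reactions. Reconcile the 30 bottles with the 50 lubricants in Section 6, and state which arm or arms use lubricant.

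The cost is small: a few sentences and, at most, one line on an existing form. A few more men must be followed, and the device estimate may turn out less favourable.
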